5.13.2. EuroQol EQ-5D-5L: Health State Utilities

Summary statistics for the index and VAS will be calculated for each assessment period by treatment arm. The EQ-5D 5L responses for each item will be summarized by frequency and corresponding percentages by treatment arm. Mean change from baseline will be estimated for the EQ-5D-5L index value and the EQ VAS self-rated health score using longitudinal MMRM regression models and will include independent variables treatment, visit, treatment*visit, and baseline. A negative change from baseline will indicate improvement.

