4.2. Secondary Objectives

Part A: There is no secondary objective planned for Part A.

Part B: Secondary objectives of Part B are to compare ramucirumab administered in combination with erlotinib versus placebo administered in combination with erlotinib for:

- safety and toxicity profile
- overall survival (OS)
- objective response rate (ORR) (complete response [CR] + partial response [PR])
- disease control rate (DCR) (CR + PR + stable disease [SD])
- duration of response (DOR)
- pharmacokinetics (PK) and immunogenicity of ramucirumab
- patient-reported outcomes (PROs; using Lung Cancer Symptom Scale [LCSS] and EuroQol 5-dimension, 5-level questionnaire [EQ-5D-5L])
- Drug-Drug Interaction (DDI) substudy to assess the pharmacokinetics of erlotinib with and without ramucirumab

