5.3.3. Patient-Reported Outcome Analysis Variables

Definitions of variables for PRO analyses are listed below alphabetically.

- Average Symptom Burden Index (ASBI) is calculated as the mean of the 6 symptom items of the LCSS. The ASBI will not be computed for a patient if he/she has one or more missing values for the 6 items. Refer to Section 10.2.1 of the protocol for the definition of the LCSS.
- EQ-5D-5L index score is calculated as recommended by EuroQol (EQ-5D-5L User Guide, www.euroqol.org). Index score and visual analog scale (VAS) will be calculated for each assessment period as per current recommendations (van Hout et al. 2012). The index score is calculated from a set of item weights to derive a score of -0.285 to 1, with 1 representing the best health status. United Kingdom (UK) weights will be applied for the base case. The index score will not be computed for a patient if he/she has one or more missing values for the 5 items.
- Change from baseline for each LCSS or EQ-5D item at any postbaseline visit is calculated by subtracting baseline assessment result from the current assessment result.
- LCSS total score is calculated as the mean of the 9 LCSS items. The LCSS total score will not be computed for a patient if he/she has one or more missing values for the 9 LCSS items.
- **Maximum change** for each LCSS item is defined as the largest decrease from baseline, which is the smallest (that is, most negative or smallest positive) non-missing value among all change from baseline values.
 - **Note.** Negative values of change from baseline (that is, decreases in the LCSS score towards the lower end of the symptom scale) indicate improvement in symptoms. For a patient and given LCSS item, if all change values are positive, the smallest positive change will be the maximum change; if at least one change value is negative, the most negative value will be the maximum change.
- Time to deterioration (TtD) for each of the 9 LCSS items, ASBI, and the LCSS total score is defined as the time from the date of randomization until the date of the first ≥15-mm increase from baseline (de Marinis et al. 2008). Alternative definitions of minimally important differences may be explored as needed. Patients without deterioration will be censored on the date of the patient's last postbaseline LCSS assessment for this item or randomization date, whichever is last.

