5.13. Patient-Reported Outcome Analyses

There is no PRO analysis planned for Part A. Descriptive analyses with each PRO instrument will be performed for Parts B and C.

For each instrument, percentage compliance will be calculated as the number of completed assessments divided by the number of expected assessments (that is, patients still on study and alive). Percentage compliance will be summarized by treatment arm and overall. Reasons for noncompliance will be described.

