5.13.1. Lung Cancer Symptom Scale

The LCSS assessments will be used primarily to calculate TtD for each of the 9 items, ASBI, and LCSS total score as defined in Section 5.3.3.

- The Kaplan-Meier method will be used to estimate parameters for time-to-event analyses on each treatment arm. Kaplan-Meier curves by treatment arm will be produced.
- HRs for treatment effect and their 2-tailed 95% CIs will be estimated using the Cox PH model stratified identically to the stratified log-rank tests. A Forest plot of the estimated HRs and their 95% CIs will be generated.
- The LCSS data will be summarized descriptively by baseline and cycle for actual measurement and change from baseline by treatment arm. For the LCSS (each item, ASBI and Total LCSS), maximum improvement over baseline is defined as the largest magnitude decrease from baseline. The analysis of maximum improvement will be conducted to compare the study treatment arms for each score using analysis of covariance (using only baseline score as a covariate) and the Mann-Whitney-Wilcoxon test. Percentage of patients who improved, remained stable, or worsened will be reported. Additionally, mean change from baseline will be estimated using Mixed effect Model Repeat Measurement (MMRM) regression and will include independent variables treatment, visit, treatment*visit, and baseline. A negative change will indicate improvement.

Additional exploratory analyses, including pattern mixture model as a sensitivity analysis to assess missingness, subgroup analysis, association with clinical outcomes, time to sustained deterioration, and predictive modeling, may be performed as deemed appropriate.

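### SAP Section 5.13.2 reads a negative change in the EQ-5D-5L index as improvement, although Section 5.3.3 scores the index with 1 as best health

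*SAP*

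**What the plan says.** Section 5.13.2 of the SAP models mean change from baseline in two EQ-5D-5L scores, the index value and the EQ VAS, by MMRM with treatment, visit, their interaction and baseline. It then gives the reading rule: "A negative change from baseline will indicate improvement".

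Section 5.3.3 defines the index. Item weights are used to "derive a score of -0.285 to 1, with 1 representing the best health status", so a higher index means better health. The same section defines change from baseline, which "for each LCSS or EQ-5D item at any postbaseline visit is calculated by subtracting baseline assessment result from the current assessment result".

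For the other instrument, the LCSS, Section 5.3.3 explains why negative changes are favourable: "decreases in the LCSS score towards the lower end of the symptom scale) indicate improvement in symptoms". Section 5.13.1 accordingly ends its LCSS MMRM text with "A negative change will indicate improvement".

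Section 4.2 lists, among the Part B secondary objectives, "patient-reported outcomes (PROs; using Lung Cancer Symptom Scale [LCSS] and EuroQol 5-dimension, 5-level questionnaire [EQ-5D-5L". Section 5.13 describes the PRO work this way: "Descriptive analyses with each PRO instrument will be performed for Parts B and C".

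**The concern.** The two instruments run in opposite directions. A lower LCSS score means fewer symptoms, whereas a higher EQ-5D-5L index means better health. The SAP nevertheless gives both the same rule for reading the sign of a change. It gives a reason for that rule only for the LCSS, where the rule is right.

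The EQ-5D-5L is one of the two PRO instruments named in the Part B secondary objectives, and the sentence in Section 5.13.2 is the only explicit rule in the SAP for the sign of an index change. If it were carried into table footnotes, figure labels or report text, a decline in health utility would be presented as a gain. The comparison of arms would be reversed with it: the arm with the more negative mean change would be described as having improved more. Because the LCSS and EQ-5D-5L sections state the same rule, a reader comparing them would get no warning that one of them is reversed.

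**Working it through.** The SAP gives no numerical figure to reproduce here. The check sets its definitions side by side and follows the sign.

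**Inputs**

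| Item | Value | SAP section |
|---|---|---|
| Best index value | 1 | 5.3.3 |
| Lowest index value | -0.285 | 5.3.3 |
| Change from baseline | current minus baseline (worded for items) | 5.3.3 |
| Scores modelled | index and EQ VAS | 5.13.2 |
| Rule for the sign | negative = improvement | 5.13.2 |

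**Step 1: range of the index.** 1 - (-0.285) = 1.285.

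**Step 2: a patient who starts at the best state (index 1).** Possible changes run from -0.285 - 1 = -1.285 to 1 - 1 = 0. Every non-zero change is negative, and every one is a loss of health. The rule calls each of them an improvement, and calls the worst possible fall, -1.285, the largest improvement.

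**Step 3: a patient who starts at the lowest state (index -0.285).** Possible changes run from -0.285 - (-0.285) = 0 to 1 - (-0.285) = +1.285. Every non-zero change is positive, and every one is a gain. Under the rule none of them counts as an improvement.

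**Step 4: any other baseline.** Since higher is better and change is current minus baseline, a positive change is a gain and a negative change is a loss wherever the patient starts. The rule therefore mislabels every non-zero change in the index. The same holds for mean changes, which are what the MMRM estimates, and so for the direction in which a difference between arms is described.

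**Step 5: can another reading rescue the sentence?**

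- *It concerns the five EQ-5D items.* Section 5.13.2 summarises the items by frequency and percentage only. The sentence directly follows the MMRM of the index and VAS.
- *It concerns the VAS alone.* Nothing limits it to the VAS, and the sentence before it names the index first.
- *Change in the index is baseline minus current.* No section says so. The only definition given states that change "is calculated by subtracting baseline assessment result from the current assessment result".
- *The text is damaged or redacted.* The sentence is complete, with no gap.

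No calculation is made for the EQ VAS, because the SAP does not state its direction.

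**The case against.** The contradiction itself is hard to dispute. The case on the other side concerns its weight.

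- *Nothing computed depends on the sentence.* The MMRM estimates, their signs and their confidence intervals are the same with or without it. Time to deterioration is defined for the LCSS only, so no planned EQ-5D-5L threshold or event analysis uses the sign. The PRO analyses are descriptive and lie outside the PFS-then-OS testing. All of this stands, and it limits the point to interpretation and reporting.
- *Section 5.3.3 already gives the right orientation, so an attentive reader would not be misled.* This stands in part. Section 5.3.3 says which end of the index is best, but it gives no rule for the sign of an index change that competes with the one in Section 5.13.2. Misreporting is a possibility, not a certainty, but a prespecified plan should not leave its reader to overrule it.
- *The sentence speaks of change from baseline, not of a treatment contrast.* True. The reversed comparison of arms is a consequence, not something the SAP states. It follows directly once each arm's change is read with the wrong sign.
- *The ±1.285 limits are extremes for a single patient, whereas the model estimates means.* True. They show that the rule is reversed across the whole scale and are not an estimate of likely impact.
- *The change definition is worded for items, not for the index.* True, so applying it to the index is an inference. It is the natural reading, and nothing in the SAP points the other way.

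**Conclusion.** The concern holds for the EQ-5D-5L index. Given the scoring in Section 5.3.3 and change taken as current minus baseline, the sign rule in Section 5.13.2 is the wrong way round for every non-zero change. The conclusion rests on one assumption: that the change definition worded for items also applies to the index.

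The size is limited. No data, model, estimate or interval is affected, and neither are PFS or OS inference or the type I error. What is at risk is the direction in which the index result of a named Part B secondary outcome is described. Nothing is concluded about the EQ VAS. That the sentence was carried over from the LCSS section is plausible, since the model terms match and the wording is nearly the same, but this is inference and the finding does not need it. The sentence should be corrected.

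**What to change.** 1. In Section 5.13.2, replace the closing sentence with one limited to the index: *For the EQ-5D-5L index, a positive change from baseline indicates improvement.*
2. In the same section, state the direction of the EQ VAS in its own sentence, after confirming it against the instrument.
3. In Section 5.3.3, extend the definition of change from baseline, now worded for items, to name the EQ-5D-5L index and the EQ VAS.
4. Keep the rule that a negative change is an improvement for the LCSS only, and align any EQ-5D-5L table footnotes and figure labels with the corrected text.

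The cost is one or two sentences in Section 5.13.2, a few words in Section 5.3.3, and a check of output footnotes and labels. Data collection, model and design stay as they are.

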5.14. Pharmacokinetics and Immunogenicity

There is no PK analysis or immunogenicity analysis planned for Part A.

5.14.1. Pharmacokinetics

In Part B, serum concentrations of ramucirumab prior to infusion (minimum or trough concentration $[C_{min}]$) and at 1 hour post-end of ramucirumab infusion (approximately maximum or peak concentration $[C_{max}]$) will be summarized using descriptive statistics. Additional analysis utilizing a population PK (PopPK) approach based on an established PopPK model may also be conducted if deemed appropriate. Relationships between ramucirumab exposure and measures of efficacy and safety will be explored. Detailed exposure-response analysis plan is described separately.

In Part C, for Ramucirumab, C_{min} and concentrations at 1 hour post end of infusion (approximately maximum concentration $[C_{max}]$) will be summarized by descriptive statistics. Additional analysis utilizing the population PK approach may also be conducted if deemed appropriate. Relationships between ramucirumab exposure and measures of efficacy and safety may be explored.

5.14.1.1. Drug-Drug Interaction Substudy

In the DDI substudy, PK parameters of erlotinib will be calculated by non-compartmental analysis and will be summarized using descriptive statistics. The effect of concomitant ramucirumab on PK of erlotinib will be assessed using erlotinib PK data from the ramucirumab plus erlotinib arm compared with erlotinib PK data from the placebo plus erlotinib arm. All patients with valid PK parameters (AUC and C_{max}) will be included in the analysis. A two-sample t-test will be used to analyze the log-transformed PK parameters of AUC and C_{max} . Means and 90% CIs for the differences of AUC and C_{max} between the 2 treatment arms in log scale were estimated, then transformed back to the original scale to estimate the ratio of geometric means and 90% CIs for the comparison (ramucirumab + erlotinib arm versus erlotinib arm).

5.14.2. Immunogenicity

For immunogenicity analyses, the number and percentage of patients with positive ramucirumab antibody response will be summarized per part. Additional efficacy or safety analyses may be performed in the subgroup of patients who are identified as treatment-emergent anti-drug antibodies (ADA) positive. The antibody response and any alteration in ramucirumab PK may

also be explored, as well as any relationship with experiencing an infusion reaction. Further exploratory analyses may be performed as appropriate.

5.15. Safety Evaluation

5.15.1. Dose-Limiting Toxicity

Dose-limiting toxicity (DLT) will be evaluated for Part A only.

DLT definitions include:

- Grade ≥4 anemia
- Grade ≥3 thrombocytopenia
- Grade ≥3 febrile neutropenia
- Grade 4 neutropenia lasting >7 days
- Elevated urine protein of ≥ 3 g/24 hour
- Grade 4 or refractory hypertension
- Grade ≥3 nonhematologic toxicity excluding electrolyte abnormality or Grade 3 skin rash

An Assessment Committee (AC) will be established as a Lilly internal review committee independent from the study team and will follow an approved AC Charter. The AC will evaluate the DLT analysis and provide consultation and recommendation to the study team with regards to the starting dose of Part B (refer to Section 9.4.1 of the protocol).

The recommended dose of ramucirumab in the Part B population will be decided based on the following rules:

- If the proportion of patients experiencing DLT is < 33% (0 or 1 patient with any DLT) for DLT-eligible patients from each of the cohorts during the first 2 cycles, the ramucirumab starting dose in Part B will be 10 mg/kg every 2 weeks.
- If the proportion of patients experiencing DLTs is $\ge 33\%$ (2 or more patients with any DLTs) for DLT-eligible patients from any of the cohorts during the first 2 cycles, the ramucirumab starting dose in Part B will depend on AC recommendation.

The study team could request an earlier AC review of the data generated before the planned database lock. For example, in case each cohort enrolled 5 DLT-evaluable patients but DLT is not observed during the DLT assessment period in these patients, an earlier data review by AC could be initiated by the study team to proceed accordingly.

Upon review of safety data, AC may recommend one of the following:

- To start enrollment in Part B with the starting dose of 10 mg/kg every 2 weeks
- To enroll 3 additional patients at 10 mg/kg every 2 weeks and reassess the dose tolerability once the additional 3 patients complete the DLT Assessment Period
- To start enrollment in Part B with the starting dose of 8 mg/kg every 2 weeks
- To stop the study

Summary of reasons for DLT non-evaluable patients will be reported. A patient listing of all DLTs will be provided.

5.15.2. Exposure

The following exposure-related variables will be reported for each part as specified:

• Exposure:

- For both ramucirumab and erlotinib duration of treatment; number of patients with dose adjustments, i.e., dose reduction, dose delay (ramucirumab only), and dose omission (Parts A and B separately)
- For both ramucirumab and gefitinib duration of treatment; number of patients with dose adjustments, i.e., dose reduction, dose delay (ramucirumab only), and dose omission (for Part C Period 1 only)
- For both ramucirumab and osimertinib duration of treatment; number of patients with dose adjustments, i.e., dose reduction, dose delay (ramucirumab only), and dose omission (for Part C Period 2 only)
- o For erlotinib: number of patients received < one week of treatment, \geq one week of treatment, \geq two weeks of treatment, \cdots , x weeks of treatment, and mean, standard deviation
- o Note: Patient is considered to have received a week of therapy after receiving at least seven doses of study drug ERLOTINIB either partial or complete.
- \circ For ramucirumab only: number of infusions received; number of patients completing < one infusion, \ge one infusion, \ge two infusions, \cdots , x infusions, and mean, standard deviation
- \circ For gefitinib: number of patients received < one week of treatment, \ge one week of treatment, \ge two weeks of treatment, \cdots , x weeks of treatment, and mean, standard deviation
- o For osimertinib: number of patients received < one week of treatment, \ge one week of treatment, \ge two weeks of treatment, \cdots , x weeks of treatment, and mean, standard deviation
- Reasons for dose adjustments and dose delays for ramucirumab, dose reductions and dose omissions (scheduling conflict, AE summarized by PT) for each

The following exposure-related variables will be reported using summary statistics (number of patients, mean, standard deviation, median, 1st and 3rd quartiles, minimum, and maximum) by treatment arm:

• Dose intensity: cumulative dose; weekly dose intensity; relative dose intensity, overall weekly dose intensity, overall relative dose intensity.

Details of study drug administration will be included in patient listings.

5.15.3. Adverse Events

All AEs will be summarized by MedDRA System Organ Class (SOC) and PT. The incidence and percentage of patients with at least one occurrence of a preferred term will be included, according to the most severe National Cancer Institute - Common Terminology Criteria for Adverse Events Version 4.0 (NCI-CTCAE v4.0) grade.

Unless otherwise specified, when summarized by PT, AEs will be presented in decreasing frequency of PT across treatment arms; when summarized by SOC and PT, AEs will be presented in decreasing frequency of PT within SOC across treatment arms. If more than one AE is recorded for a patient within any SOC or PT term, the patient will only be counted once on the most severe grade and the closest relationship to treatment.

A summary of AEs will be presented for Parts A, B and C separately.

5.15.3.1. Overall Summary of Adverse Events

An overall summary of AEs will be provided to summarize the following categories using frequency counts and percentages:

- patients with at least one TEAE, SAE, or NCI-CTCAE Grade ≥3 TEAE
- patients with AEs that led to death (on study treatment, within 30 days of discontinuation from study treatment)
- patients with AEs that led to discontinuation
- patients with SAEs that led to discontinuation

The summary will be provided for regardless of study drug causality, and repeated for events deemed by the investigator to be possibly related to study treatment.

A patient listing of all AEs will be provided.

5.15.3.2. Treatment-Emergent Adverse Events

The following summaries of TEAEs will be provided, with treatment comparison using Fisher's exact test (*repeat for events deemed by the investigator to be possibly related to study medication, [†]include consolidated summary):

- by SOC and/or by PT*†
- by maximum NCI-CTCAE grade and by SOC and/or by PT*†

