Statistical Analysis Plan for Clinical Study I4T-MC-JVCY

A Multicenter, Randomized, Double-Blind Study of Erlotinib in Combination with Ramucirumab or Placebo in Previously Untreated Patients with *EGFR* Mutation-Positive Metastatic Non-Small Cell Lung Cancer

NCT02411448

Approval Date: 13-Dec-2018

1. Statistical Analysis Plan for Clinical Study: I4T-MC-JVCY: A Multicenter, Randomized, Double-Blind Study of Erlotinib in Combination with Ramucirumab or Placebo in Previously Untreated Patients with *EGFR*Mutation-Positive Metastatic Non-Small Cell Lung Cancer

Confidential Information

The information contained in this Statistical Analysis Plan (SAP) is confidential and the information contained within it may not be reproduced or otherwise disseminated without the approval of Eli Lilly and Company or its subsidiaries. This document and its associated attachments or appendices are subject to United States Freedom of Information Act Exemption 4.

Ramucirumab (LY3009806) Non-Small Cell Lung Cancer

This is a multicenter, randomized, double-blind, Phase 3 study that will compare the efficacy and safety of treatment with erlotin b (150 mg daily) and ramucirumab (10 mg/kg every 2 weeks) versus erlotinib (150 mg daily) and placebo (10 mg/kg every 2 weeks) in previously untreated patients with *EGFR* mutation-positive metastatic NSCLC. Treatment will continue until disease progression, unacceptable toxicity, or another permitted reason for study discontinuation. This Phase 3 part (Part B) is preceded by a Phase 1b part (Part A) to assess the safety and tolerability for the combination of ramucirumab plus erlotin b. In addition, Part C, an open-label, 2-period, single-arm, exploratory cohort is added to the main protocol.

Eli Lilly and Company Indianapolis, Indiana USA 46285 Protocol I4T-MC-JVCY Phase 1b/3

Statistical Analysis Plan (SAP) Version 3 electronically signed and approved by Lilly on date provided below.

SAP Version 2 electronically signed and approved by Lilly: 31 May 2018 SAP Version 1 electronically signed and approved by Lilly: 17 April 2015

Approval Date: 13-Dec-2018 GMT

2. Table of Contents

Section	Page
1. Statistical Analysis Plan for Clinical Study: I4T-MC-JVCY: A Multicenter, Randomized, Double-Blind Study of Erlotinib in Combination with Ramucirumab or Placebo in Previously Untreated Patients with EGFR Mutation-Positive Metastatic Non-Small Cell Lung Cancer	1
2. Table of Contents	2
3. Revision History	5
4. Study Objectives	7

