5.15.6. Hospitalizations and Transfusions for Parts B and C

The frequency and percentage of patients with any hospitalizations experienced during the study treatment period or within 30 days of treatment discontinuation will be summarized by treatment arm. Hospitalization incidence rates will be compared between the treatment arms using Fisher's exact test. In addition, total number of days in hospital and admissions will be summarized and compared using the Wilcoxon rank sum test. These will be further characterized by reason.

Note. Discharge date will be imputed with last contact date for hospitalizations that are still ongoing at time of analysis.

The frequency and percentage of patients with any blood transfusions experienced during the study treatment period or within 30 days of treatment discontinuation follow-up period will be summarized by treatment arm. Transfusions will be further characterized by transfused blood product (for example, packed red blood cells, platelets, fresh frozen plasma, or whole blood).

The proportions of patients having blood transfusions will be compared between the treatment arms using Fisher's exact test.

Details of hospitalizations and transfusions will be included in patient listings.

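### Treatment-emergent adverse events, hospitalizations and transfusions in Part B are compared only as crude proportions or totals, with no time-at-risk comparison beside them, although treatment runs to progression

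*SAP*

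**What the plan says.** The study description on the SAP's title page gives treatment no fixed length: "Treatment will continue until disease progression, unacceptable toxicity, or another permitted reason for study discontinuation".

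The safety measures are counts of patients. Section 5.15.3 states: "The incidence and percentage of patients with at least one occurrence of a preferred term will be included". Section 5.15.3.2 adds the between-arm test for TEAEs by system organ class or preferred term and by maximum grade: "with treatment comparison using Fisher's exact test".

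Section 5.15.6 sets the hospitalization measure as "The frequency and percentage of patients with any hospitalizations experienced during the study treatment period or within 30 days of treatment discontinuation", and then says: "Hospitalization incidence rates will be compared between the treatment arms using Fisher's exact test". Despite the word rates, the quantity is a percentage of patients. For burden, "total number of days in hospital and admissions will be summarized and compared using the Wilcoxon rank sum test". For transfusions, "The proportions of patients having blood transfusions will be compared between the treatment arms using Fisher's exact test".

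Section 5.15.2 tabulates treatment duration, infusions, weeks of treatment and dose intensity ("The following exposure-related variables will be reported for each part as specified"), but no safety analysis uses exposure as a denominator. The overall adverse event summary (5.15.3.1), deaths, SAEs and adverse events of special interest (5.15.4), safety subgroups (5.15.8) and registry tables (5.19) add no person-time, time-to-first-event or fixed-window analysis.

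**The concern.** A patient on treatment longer has more time to have a first event. When treatment ends at progression, and one arm is expected to progress later, an ever/never proportion mixes two things: how often events occur per month on treatment, and how many months were observed. The same holds for total admissions and hospital days.

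Section 4.2 lists the safety and toxicity profile as a secondary comparison, and Section 5.2 sets a two-sided 0.05 level for tests of treatment effects unless otherwise stated. The p-values will therefore be read as evidence about toxicity. If the trial succeeds as designed, they cannot distinguish a higher event rate from longer exposure, and nothing else in the plan does.

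**Working it through.** **Inputs from the SAP (5.1.2, 5.2).** About 225 patients per arm, 270 PFS events, HR 0.71, one-sided alpha 0.02499, control median PFS 11 months, exponential survival; two-sided 0.05 for the safety tests.

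**Inputs assumed.** Time on treatment equals PFS time. The first-event hazard λ is constant and equal in both arms. Accrual is uniform over 24 months. λ is 0.02 to 0.04 per month.

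**The plan's own figures first.**
- Power (Schoenfeld): √270/2 × |ln 0.71| − 1.960 = 2.814 − 1.960 = 0.854, so power is 80.3%. This agrees with the stated 80%.
- Median in the combination arm: 11/0.71 = 15.49 months, a gain of 4.49. This agrees with the stated 4.5 months.
- Progression hazards: μ0 = ln 2/11 = 0.0630 and μ1 = 0.71 × 0.0630 = 0.0447 per month. Mean uncensored times are 15.9 and 22.4 months.

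**At the primary cut.** With entry at month a, uniform on 0 to 24, and a cut at month C, the expected number of PFS events reaches 270 at C = 30.5. Averaged over a:
- mean exposure = (1 − e^(−μ(C−a)))/μ, which gives 10.4 versus 12.1 months;
- proportion with an event = λ/(λ+μ) × (1 − e^(−(λ+μ)(C−a))).

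**With full follow-up** the proportion is λ/(λ+μ). For λ = 0.02: 0.02/0.0830 = 24.1% and 0.02/0.0647 = 30.9%.

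Rejection by the two-sided Fisher test at 0.05, enumerated exactly for 225 per arm:

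| Setting | λ per month | Shorter-exposed arm | Longer-exposed arm | Difference (points) | Fisher rejects |
|---|---|---|---|---|---|
| 270-event cut | 0.02 | 18.0% | 20.6% | 2.6 | 8.6% |
| 270-event cut | 0.04 | 31.5% | 35.6% | 4.1 | 13.1% |
| Full follow-up | 0.02 | 24.1% | 30.9% | 6.8 | 32.8% |

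Simulation of the same model gives 8% to 10% at 0.02, 14% at 0.04, and 33% to 35% with full follow-up. Accrual of 18 or 30 months barely changes the differences (2.5 to 2.7 and 4.1 to 4.2 points). With truly equal proportions, Fisher's test rejects in 3.1% to 4.3% of trials, and nearly all the extra rejections go against the longer-exposed arm. In simulation, Wilcoxon on admissions rejects in 9% to 14% at 0.02 to 0.03 admissions per month. A rate comparison under this same constant-hazard model rejects in about 4% to 6%.

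**Where the effect fades.**
- Early onset: if the event can occur only in the first 3 months, full follow-up gives 30.0% versus 30.8%, or 50.0% versus 51.2%.
- Toxicity discontinuation: an extra 0.01 per month in the combination arm cuts the difference at the primary cut from 2.6 to 1.1 points (λ = 0.02) and from 4.1 to about 2 points (λ = 0.04). An extra 0.0630 − 0.0447 = 0.018 per month removes it.

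**What a rate ratio does in the opposite case.** Take an event possible only in the first 2 months, with identical hazard in both arms and 30% of patients affected. In simulation at the primary cut, a constant-hazard rate test rejects in about 18% of trials, nearly all in favour of ramucirumab (mean rate ratio 0.88). With full follow-up it rejects in 44% to 49% (ratio 0.71). Fisher's test rejects in about 4% in both.

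**The case against.** Four points on the other side have weight.

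First, Fisher's test is valid for its own question: whether the proportion of patients with an event over the treatment course differs. In the model above those proportions do differ, so rejection is not an error for that hypothesis. This stands. What is missing is a comparison of the other quantity, events per time at risk.

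Second, a reader might infer that the Fisher p-values should go and rate ratios take their place. The early-onset result argues against that: a constant-hazard rate test then errs at least as badly, in the direction that hides toxicity. Neither measure is better throughout.

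Third, the size depends on exposure tracking PFS. Treatment also ends for unacceptable toxicity and other permitted reasons, which the model leaves out. This stands as a limit on size. It is also a reason to measure time at risk, because the direction and extent of any imbalance are not known in advance.

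Fourth, exposure is already tabulated, and Section 5.16 sets no prespecified safety stopping rule that these p-values would trigger. Both are true, but a separate exposure table does not let a reader adjust a Fisher p-value.

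Two wider readings go beyond the text. Section 5.15.4 names no test for SAEs or adverse events of special interest, so there is no misleading p-value there, only crude counts. And the window of 30 days after discontinuation is stated for hospitalizations and transfusions, not for TEAEs, whose definition in 5.3.2 has no stated end.

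**Conclusion.** The point holds as a gap in the safety analysis, not as an invalid test. For TEAEs, hospitalizations and transfusions, the only planned between-arm comparisons ignore time at risk, in a design that assumes one arm stays progression-free about 4.5 months longer at the median.

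Under constant, equal event rates and exposure equal to PFS time, the distortion is modest at the primary analysis, where about 40% of patients are still censored. It grows at later cuts, for instance if safety is tabulated again at the final OS analysis at about 300 deaths. The full-follow-up figures are an upper range and do not describe the primary analysis.

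A reader might conclude that the plan is bound to show an excess against ramucirumab. The documents do not support that, because early-onset events and unequal toxicity discontinuation can each remove it. The primary PFS test is unaffected.

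**What to change.** Keep the Fisher and Wilcoxon comparisons as planned. Add beside them, for the Part B safety population:

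- In 5.15.3.2, 5.15.4 and 5.15.6: a time-at-risk comparison of TEAEs by preferred term, Grade 3 or higher TEAEs, SAEs, adverse events of special interest and any hospitalization. Use either time to first event with a hazard ratio and 95% CI, or exposure-adjusted incidence rates (first events per patient-time at risk) with a rate ratio and 95% CI. State when time at risk ends, including for TEAEs.
- In 5.15.6: admissions and hospital days per patient-month, from a negative binomial or Poisson model with log time at risk as offset.
- One sentence on reading them: crude and time-at-risk results are interpreted together, and constant-hazard rate ratios are not used alone for events concentrated in the first cycles.

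The cost is SAP wording and extra tables from dosing and event dates already collected, with no design change. The downside is more output and a known weakness: constant-hazard rate ratios understate early-onset toxicity in the longer-exposed arm. Time to first event does not need a constant hazard and is the safer choice where onset is early.
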